1.4 Sample Size and Power

The study design allows for sufficient power for both the primary and top secondary outcomes. Numerical simulations based on multivariate normal vectors ([Appendix 2](#)) were conducted to estimate power for the primary treatment comparison based on the following assumptions about events rates described in **Table 1.4.1**

Table 1.4.1. Assumptions about Event Rates for Primary Outcome

Ranked tier at 12-month endpoint (6 month for 6 MWT)	Control	Treatment
Death total	8%	6.8%
Death without hospitalization	4%	3.4%
Death with hospitalization	4%	3.4%
Hospitalizations in survivors		
1	6%	4.8%
2	3%	2.4%
3 or more	1%	0.8%
Change in 6 Minute Walk Test	Mean = 0 SD = 90	Mean = 18 SD = 90

With 3014 participants (1507 per arm) and 2.5% annual loss to follow-up for clinical outcomes and 15% of individuals with missing 6MWT at 6 months (unable to perform or lost to follow-up), projected simulations estimate 90% power at an overall two-sided significance level of 0.01, accounting for one interim analysis as described in [Section 7.1](#).

For the top secondary composite, there is an assumed event rate of 0.0128 per month in the control arm which represents conservative 75% discounting of the event rate obtained by the FCM meta-analysis [[Anker 2015](#)]. The anticipated hazard ratio (HR) was set at 0.80 (20% reduction). Uniform enrollment was assumed over the period of 30 months, with an anticipated minimum follow-up of 12 months (required minimum of 6 months), anticipated maximum follow-up of 42 months (no required maximum), and monthly loss to follow-up of 0.0021 (2.5% annualized). With these assumptions, 1500 per study arm (3000 total) provides 90% power to reject the null hypothesis of no difference between treatment arms when tested at an overall two-sided level of significance $\alpha=0.05$, accounting for one interim analysis as described in Section 8.10 of the CSP. This results in a total of 771 participants with events (in case of multiple events experienced by a participant, only their first one will be counted towards the 771) necessary to achieve the desired power. Thus, the trial has the potential opportunity to be stopped at a point where the projected number of participants reaches 771 events, but no earlier than the last participant reaching 12 months of follow-up.

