In order to maintain an overall alpha of 0.01 and account for interim analysis we will use a two-sided alpha of 0.0099 for the final analysis of the primary endpoint.

At the request of the FDA, the overall alpha for the top secondary endpoint was changed from 0.05 to 0.04. In order to maintain an overall alpha of 0.04 and account for interim analysis we will use a two-sided alpha of 0.0399 for the final analysis of the top secondary endpoint.

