5.1 Primary Outcome

The primary outcome follows an ordinal scale of clinical severity comprised of 1) confirmed death at one year, 2) number of confirmed hospitalizations for heart failure evaluated at one year; or 3) change in 6MWT from baseline evaluated at 6 months.

We will rank all participants from the lowest to the highest based on their 12-month experience, regardless of their treatment assignment.

Each participant from the treatment arm gets ranked/compared with each participant from the control arm based on the 12-month experience for Death and Hospitalizations for heart failure and 6 month results for change in 6MWT to determine treatment response per the following hierarchy:

1. Death

If both die, the one who survives longer is better off;
If one dies and one does not, the one that survives is better off;
If neither dies, examine hospitalizations for heart failure.

2. Hospitalizations for heart failure

The one with fewer hospitalizations is better off
If neither has been hospitalized for heart failure or the number heart failure hospitalizations is equal, compare change in 6MWT.

3. Change in 6MWT

The one with higher change in 6MWT is better off;

Any ties that cannot be resolved by change in 6MWT remain as ties.

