5.3.1 Nonparametric Test of FCM vs. Placebo for Primary Composite

The null hypothesis being tested is that a randomly chosen participant in the treatment arm is equally likely to be ranked better or worse than a randomly chosen participant in the control group. The two-sided alternative is that the participant is not equally likely to be ranked better or worse.

In addition to performing the test, we will estimate the probability that a participant in the treatment arm has a better rank than a participant in the control arm and its corresponding confidence interval.

The main comparison will be conducted using the Wilcoxon-Mann-Whitney test in ITT population relying on multiple imputation model as summarized in Section [4.4.1](#).

The above comparison of participants in the treatment versus control arms is equivalent to ranking all participants according to their experience. At one end of the ranking are participants with the best experience - those alive and not hospitalized for worsening heart failure ordered according to their improvement in 6MWT; at the opposite end are those who die ordered according to their survival time. Those participants alive but hospitalized are in the middle, ordered according to their number of hospitalizations for worsening heart failure and then by their change in 6MWT. The non-parametric Wilcoxon-Mann-Whitney test sums the ranks of those in the treatment arm and compares them with the sum of ranks in the control arm.

Win-Ratio and its confidence intervals will be calculated to aid in interpretation of the results for primary efficacy analysis. The unmatched pair win ratio will be calculated by adding all wins from treatment group and dividing it by all wins from placebo group. The confidence interval will be calculated using the supplementary material for the reference ([Pocock 2012](#)).

In all analyses, the number of hospitalizations (and the number of days in the hospital in the sensitivity analysis described in Section 5.3.1.1) will be adjusted for the time in follow-up. This will be accomplished by dividing the observed number by time at risk in years. For individuals who complete the pre-specified 12 months of follow-up, time at risk equals 1. For all others, it is equal to the fraction of 12 months that the person remained in the study.

5.3.1.1 Sensitivity Analysis (Additional Layer to Hierarchy) for Nonparametric Test of FCM vs. Placebo for Primary Composite

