5.5 Secondary Outcomes

All other secondary outcomes are listed and defined below. These secondary outcomes will be tested in the order listed below and are considered as supportive in the assessment of the effect size attributable to FCM and will be analysed in ITT only and without a multiplicity adjustment.

- (1) Mean change in 6MWT distance from baseline to 12 months will be compared using linear regression adjusting for baseline value of 6MWT distance and region. We will not adjust for other baseline covariates.
- (2) Time to CV deaths or intervention for worsening heart failure (hospitalization or urgent heart failure visits) defined as time from randomization to the earliest of confirmed CV death or confirmed intervention for worsening heart failure will be compared using the Cox proportional hazards model.
- (3) Time to CV deaths or CV hospitalizations defined as time from randomization to the earliest of confirmed CV death or confirmed CV hospitalization will be compared using the Cox proportional hazards model.
- (4) Time to CV deaths defined as time from randomization to confirmed CV death (deaths confirmed as “Unknown” type will be included in the CV death counts) will be compared using the Cox proportional hazards model.

- (5) Time to non-cardiovascular deaths defined as time from randomization to confirmed non-CV death will be compared using the Cox proportional hazards model.
- (6) Time to first confirmed hospitalization for myocardial infarction (MI) defined as time from randomization to the earliest confirmed hospitalization for MI will be compared using the Cox proportional hazards model.
- (7) Time to first confirmed hospitalization for stroke defined as time from randomization to the earliest confirmed hospitalization for stroke will be compared using the Cox proportional hazards model.
- (8) Time to first confirmed hospitalization for other CV event defined as time from randomization to the earliest confirmed hospitalization for other CV event will be compared using the Cox proportional hazards model.
- (9) Time to first confirmed urgent heart failure visit defined as time from randomization to the earliest confirmed urgent heart failure visit will be compared using the Cox proportional hazards model.

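### The primary Wilcoxon test ranks raw 6MWT change without adjusting for baseline distance or prognostic covariates, and so gives up a modest amount of precision

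*Combined protocol and SAP*

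**What the plan says.** - **Primary test.** SAP v1.3, 5.3.1: "The main comparison will be conducted using the Wilcoxon-Mann-Whitney test in ITT population". The section names no baseline distance and no covariate. Protocol 8.6 specifies the same test.
- **Third tier.** SAP 5.1: "The one with higher change in 6MWT is better off". The quantity ranked is the 6-month distance minus the baseline distance.
- **Baseline distance elsewhere in the primary analysis.** Section 4.4.1 puts baseline 6MWT, treatment and region in the model that imputes missing 6-month distances. It sets participants unable to perform the test to 0 m. The imputation model does not adjust the treatment comparison.
- **6MWT regressions.** The 12-month change (5.5, item 1) is "compared using linear regression adjusting for baseline value of 6MWT distance and region". The 6-month change, which is the primary endpoint's own third tier, is treated the same way in 5.7, item 4.
- **Cox models.** Sections 4.1 and 5.3.2 stratify by region and adjust for 11 listed baseline covariates. A covariate with more than 5 missing values is dropped.
- **Design.** SAP 1.4: "With 3014 participants (1507 per arm) and 2.5% annual loss to follow-up for clinical outcomes", with "15% of individuals with missing 6MWT at 6 months"; "projected simulations estimate 90% power at an overall two-sided significance level of 0.01". At the final look, "we will use a two-sided alpha of 0.0099 for the final analysis of the primary endpoint".

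**The concern.** Subtracting baseline is not the same as adjusting for it. Through regression to the mean, participants who walk far at entry tend to show smaller changes, so raw change is negatively correlated with baseline distance. A chance difference between arms in baseline distance therefore feeds into the ranks of the confirmatory test. The 0 m rule adds to this: a living participant who cannot do the 6-month test has change equal to minus baseline, so among such participants with equal hospitalization counts the order depends only on entry distance.

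The SAP removes this noise in its regression of the same 6-month change, but not in the primary test. At stake is the width of the win-probability interval, and some power if the true effect is smaller than planned.

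**Working it through.** **1. The plan's own power figure.** The hierarchy was simulated with the Table 1.4.1 rates (deaths 8% and 6.8%; one, two, and three or more hospitalizations in survivors 6/3/1% and 4.8/2.4/0.8%; 6MWT change 0 and 18 m, SD 90), 1507 per arm, two-sided alpha 0.0099. Tiers were drawn independently, because the correlations used in the plan's simulation are not given.

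| Missing 6MWT | Unadjusted power |
|---|---|
| None | 99.8% |
| 15%, at random | about 99% |
| 15%, no treatment effect | 98% |
| 15%, ranked worst | about 95% |
| 17.5%, ranked worst | 93.5% |

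The stated 90% is not reproduced closely. It looks conservative, which fits Appendix 2's conclusion of at least 90%.

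**2. Share of pairs decided by 6MWT.** Event-free: control 1 − 0.08 − 0.10 = 0.82; treatment 1 − 0.068 − 0.08 = 0.852. Both event-free: 0.82 × 0.852 = 0.6986. Tied non-zero counts: 0.06 × 0.048 + 0.03 × 0.024 + 0.01 × 0.008 = 0.0037. Total 0.702.

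**3. The 6MWT tier alone.** With equal SD σ at both visits and correlation ρ, change has variance 2σ²(1 − ρ), and the 6-month value adjusted for baseline has σ²(1 − ρ²). The ratio is (1 + ρ)/2: 0.75 at ρ = 0.5, 0.85 at 0.7, 0.95 at 0.9. The documents do not give ρ.

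**4. The composite rank.** Share of rank variance explained by baseline distance, assuming distance is unrelated to events (baseline mean 300 m assumed for the 0 m row):

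| | ρ 0.5 | 0.6 | 0.7 | 0.8 | 0.9 |
|---|---|---|---|---|---|
| 15% missing at random | 10.8% | 8.6% | 6.4% | 4.3% | 2.2% |
| 15% set to 0 m | 7.1% | 5.8% | 4.6% | 3.5% | 2.3% |

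**5. Letting distance predict events.** Appendix 2 itself says the 6MWT stratifies risk. Short walkers then have more events (lower ranks) but regress upward in change (higher ranks), and the two partly cancel. A change SD of 90 m and baseline SD s imply ρ = 1 − 90²/(2s²): 0.37, 0.60 and 0.72 for s = 80, 100 and 120 m. With 15% set to 0 m:

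| Correlation of distance with event risk | s = 80 | 100 | 120 |
|---|---|---|---|
| 0.2 | 3.7% | 2.1% | 1.3% |
| 0.3 | 1.9% | 0.9% | 0.5% |

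At still higher ρ the gain approaches zero.

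**6. What this buys.** At exactly 90% power the expected z is 2.579 + 1.282 = 3.861. Removing a share R² of the variance gives power Φ(3.861/√(1 − R²) − 2.579) and an equivalent size of 3014/(1 − R²).

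| R² | Power | Equivalent N | Extra |
|---|---|---|---|
| 0.5% | 90.2% | 3029 | 15 |
| 2% | 90.7% | 3076 | 62 |
| 4% | 91.3% | 3140 | 126 |
| 11% | 93.5% | 3387 | 373 |

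In direct simulation at the full design effect with ρ = 0.7, adjustment moves power from 99.0% to 99.4% (missing at random) or from 94.9% to 96.0% (0 m). At 60% of the design effect the moves are 62.3% to 65.6% and 49.4% to 51.0%.

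**7. Chance imbalance.** An imbalance of one standard error in baseline distance shifts the primary z by √R²: about 0.07 at 0.5%, 0.20 at 4% and 0.33 at 11%, against a critical value of 2.58.

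**The case against.** The strongest reply is that nothing is wrong with the test. Randomization protects its type I error, chance imbalance is already part of its reference distribution, and any unadjusted test can be moved that way. Power at the design effect is already ample, and the Wilcoxon test is fixed in the protocol. All of this stands, and it makes the point one of efficiency.

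A reader might infer that the primary test is the only efficacy analysis left unadjusted. It is not. The negative binomial and modified Poisson models in 5.7 name no covariates, the responder analysis is a plain chi-square test, and the win ratio and the other hierarchical composites follow the unadjusted method. The 12-month 6MWT regression expressly excludes covariates beyond baseline distance and region. The contrast holds only with the Cox models and the 6MWT regressions.

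A reader might also infer a gain of about 15% of variance, some 530 participants (3014/0.85 = 3546). That needs a baseline-to-6-month correlation near 0.37, no link between distance and events, and no 0 m values. The last conflicts with SAP 4.4.1, and the second sits badly with Appendix 2.

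Nor can it be claimed that the remaining covariates must add a material gain: the documents give no figure for how well they predict the composite.

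**Conclusion.** The primary test leaves out baseline distance and the prognostic covariates that the SAP already uses for its Cox models and 6MWT regressions. The loss is modest: roughly 0.5–11% of the composite-rank variance from baseline distance alone, and more likely a few percent or less once the 0 m rule and a link between distance and events are allowed for. This rests on assumed correlations (baseline to 6 months about 0.5–0.9; distance to events 0–0.3), an assumed baseline mean of 300 m for the 0 m cases, and the Table 1.4.1 rates. The benefit matters mainly if the true effect falls short of plan. The documents do not support reading this as bias, an inflated error rate or a shortfall in planned power. It is a small improvement available from data already collected.

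**What to change.** Before unblinding, keep the hierarchy, ranks, null hypothesis and win probability. Compute the test and confidence interval by Koch-type randomization-based nonparametric covariance adjustment of the ranks. Adjust for baseline 6MWT distance and those section 4.1 covariates that survive the missing-data rule there, within each imputed dataset, and pool by Rubin's rule. Name this one method. A Quade-type test on residual ranks would not itself supply the win-probability interval. Report the unadjusted Wilcoxon result and the win ratio alongside.

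The cost is wording in SAP 5.3.1 and protocol 8.6 plus code. No new data are needed. If the sponsor prefers not to change the confirmatory test, the same analysis should at least be pre-specified as supportive, since none of 5.3.1.1 to 5.3.1.9 adjusts for baseline distance.

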5.3.2 FCM vs. Placebo for Top Secondary Outcome

This analysis will compare time from randomization to the first occurrence of CV death or hospitalization for heart failure. The Cox proportional hazards model will be employed to conduct this comparison. The Cox model will include treatment, region as a stratification variable and will be adjusted for pre-decided baseline covariates as noted in section 4.1. The test will be two-tailed and will be performed at an overall α of 0.04. This analysis will be performed by the ITT principle based on randomized treatment assignment and we expect adequate power to detect a pre-specified relative risk reduction of 20%.

5.3.2.1 Supportive Analysis for FCM vs. Placebo for Top Secondary Outcome

As supportive analysis, time from randomization to the first occurrence of CV death or hospitalization for heart failure will be analysed in PP using the same approach as for the primary analysis based on the ITT population.

5.3.2.2 Sensitivity Analysis (Tipping Point) for FCM vs. Placebo for Top Secondary Outcome

In case there are 5% or more participants who prematurely discontinue from the study follow-up without having an event of death or hospitalization for heart failure, and the hazard ratio obtained from the top secondary outcome analysis is between 0.85 and 1.15 inclusive, we will perform tipping point assessments to determine the sensitivity of the result obtained from the top secondary analysis to the missing data caused by participants' early discontinuation. Events will be imputed during their missed follow-up time (i.e., time from early discontinuation to trial termination visit) under various scenarios for the hazard rates for the non-completers in each treatment arm. For each scenario, 20 imputations will be performed and the results will be combined across the 20 datasets that have both the actual events and imputed events using Rubin's rule (Rubin, 1987). Hazard ratio (95% CI) and p-value will be calculated for each scenario. The goal of this analysis is to find the scenarios where the top secondary outcome results conclusion could be changed. This analysis will be conducted in the ITT population only.

5.3.2.3 Sensitivity Analysis for Russia Ukraine War Impact (censor the data after invasion) for FCM vs. Placebo for Top Secondary Outcome

As one of the two sensitivity analyses to assess the impact of the Russia-Ukraine war on the top secondary outcome, we will censor the data from Russia and Ukraine for the time from randomization to the first occurrence of CV death or hospitalization for heart failure outcome with a date after invasion (24 February, 2022). The analytic method will be the same as used for top secondary analysis. This will be conducted in the ITT population only.

5.3.2.4 Sensitivity Analysis for Russia Ukraine War Impact (exclude participants from these two countries) for FCM vs. Placebo for Top Secondary Outcome

As the second sensitivity method to assess the impact of the war on the top secondary outcome, we will exclude participants from Russia and Ukraine for comparison of the time from randomization to the first occurrence of CV death or hospitalization for heart failure outcome using the primary analytic method. This will be conducted in the ITT population only.

5.4 Subgroup Analyses for Top Secondary Outcome

Subgroup analyses will be performed for the top secondary outcome in the ITT population in order to explore whether treatment effects on the risk of developing CV events are consistent across subgroups. Subgroup analyses will be performed using the same analysis models as for the top secondary endpoints, with the addition of the subgroup factor and its interaction with treatment. The same subgroup analyses will also be repeated in the PP population.

The subgroups will be divided by categories for continuous variables. The subgroup analyses will be summarized via a forest plot and interaction p-values will be reported. We would look further into the subgroup if any interaction p-values are smaller than 0.15. Pre-specified subgroups are detailed below.

Key Subgroups of Interest include split by:

Age (<65 vs ≥65 years old),
NT-proBNP (<median vs ≥median pg/mL),
NYHA class (I and II vs III and IV),
Heart failure etiology (Ischemic, Non-ischemic, Unknown),
Ejection fraction (≤ median vs. > median),
Estimated glomerular filtration rate (<60 vs 60+ ml/min/1.73m²),
Sex (Male/Female),
Ferritin-TSAT (<100 ferritin vs ferritin ≥100-300 with TSAT<20%),
Chronic renal insufficiency (Yes/No),
Diabetes mellitus (Yes/No),
Iron deficiency anaemia (female and haemoglobin <12 g/dL or male and haemoglobin <13.5 g/dL, vs higher haemoglobin value for either sex),
BMI (<25, ≥25 to <30, and ≥30),
Region (North America, Europe (includes Russia and Georgia), Asia Pacific),
Race (White, Black, Other(American indian or Alaska native, Asian, multiple, native Hawaiian or other pacific islander, other)),
Atrial fibrillation (Yes/No),
Hospitalization for HF within past 12 months (Yes/No)

5.5 Secondary Outcomes

All other secondary outcomes are listed and defined below. These secondary outcomes will be tested in the order listed below and are considered as supportive in the assessment of the effect size attributable to FCM and will be analysed in ITT only and without a multiplicity adjustment.

- (1) Mean change in 6MWT distance from baseline to 12 months will be compared using linear regression adjusting for baseline value of 6MWT distance and region. We will not adjust for other baseline covariates.
- (2) Time to CV deaths or intervention for worsening heart failure (hospitalization or urgent heart failure visits) defined as time from randomization to the earliest of confirmed CV death or confirmed intervention for worsening heart failure will be compared using the Cox proportional hazards model.
- (3) Time to CV deaths or CV hospitalizations defined as time from randomization to the earliest of confirmed CV death or confirmed CV hospitalization will be compared using the Cox proportional hazards model.
- (4) Time to CV deaths defined as time from randomization to confirmed CV death (deaths confirmed as “Unknown” type will be included in the CV death counts) will be compared using the Cox proportional hazards model.

- (5) Time to non-cardiovascular deaths defined as time from randomization to confirmed non-CV death will be compared using the Cox proportional hazards model.
- (6) Time to first confirmed hospitalization for myocardial infarction (MI) defined as time from randomization to the earliest confirmed hospitalization for MI will be compared using the Cox proportional hazards model.
- (7) Time to first confirmed hospitalization for stroke defined as time from randomization to the earliest confirmed hospitalization for stroke will be compared using the Cox proportional hazards model.
- (8) Time to first confirmed hospitalization for other CV event defined as time from randomization to the earliest confirmed hospitalization for other CV event will be compared using the Cox proportional hazards model.
- (9) Time to first confirmed urgent heart failure visit defined as time from randomization to the earliest confirmed urgent heart failure visit will be compared using the Cox proportional hazards model.

All time to event secondary outcomes will be analysed using the same approach as in the top secondary outcome analysis based on the ITT population. To assess change from baseline, a baseline measurement and the 12-month measurement both are required.

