2 ANALYSIS SETS

2.1 Intent-to-treat (ITT) Population

The ITT population consists of all participants randomized to a treatment group in the study regardless of their compliance with the study medication. The participants are analysed in the treatment group to which they were randomized. This is the primary population of all efficacy analyses.

Any participant who gets a treatment assigned via the IXRS will be considered to have been randomized.

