4.4 Handling of Missing Data

4.4.1 Outcome Data/Dates

The primary analysis will rely on a multiple imputation model, with Markov chain Monte Carlo algorithm based on the totality of observed data. One exception to this rule will be that

individuals unable to perform the 6MWT test at 6 months i.e. those who did not perform a 6MWT or died prior to 180 days will have their value imputed as the worst possible 6MWT distance which is 0 meters. Any missing death dates will be imputed using date imputation rules in this section. A baseline 6MWT distance is needed to be able to calculate change from baseline 6MWT, hence, any missing baseline 6MWT distance will be imputed as overall mean to allow full ITT population to be included in primary analyses.

The SAS PROC MI procedure will be used for multiple imputations on the 6 month 6MWT distance, with 20 imputations. To ensure consistency in the imputed data for future possible validations, a seed number will be fixed to 1000. Baseline 6MWT, treatment and region will be included as covariates in the imputation model. We will include all observed data in the imputation model with the exception of participants unable to perform 6MWT at 6 months who will have their 6MWT distance included as 0 meters before performing multiple imputation. Imputed data set(s) will include an index variable to identify the number of imputed data. The results across the imputed datasets will be combined using Rubin's rule ([Rubin 1987](#)) to obtain one set of results for the primary analysis. These same missing data handling rules will be used for the Win-Ratio analyses. Basic statistics on the overall original data (incomplete data) and the data following imputation will be provided in the Clinical Study Report (CSR).

For secondary efficacy endpoints, missing data relating to the indicator for the confirmed composite CV outcome and/or its components will not be imputed. Any partial or completely missing date for a confirmed composite CV outcome at the time of database lock will be imputed as follows:

- If the day is missing, 15th of the month, or the randomization date (if participant randomized after 15th of the same month and same year) will be used, making sure the imputed date is not post date last known alive on end of study form;

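### The 12-month walk-test secondary endpoint is called ITT but is a complete-case regression, with no imputation or sensitivity analysis for missing 12-month walks

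*Combined protocol and SAP*

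**What the plan says.** The mean change in 6MWT distance to 12 months is item (1) of SAP v1.3 section 5.5, first in order after the top secondary outcome. It is "compared using linear regression adjusting for baseline value of 6MWT distance and region". The outcomes in this section are described as supportive and "will be analysed in ITT only and without a multiplicity adjustment". Section 2.1 defines the population: "The ITT population consists of all participants randomized to a treatment group in the study regardless of their compliance with the study medication". The last paragraph of section 5.5 then sets the completeness rule: "To assess change from baseline, a baseline measurement and the 12-month measurement both are required".

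The missing-walk rules in section 4.4.1 are written for the primary analysis and for the 6-month visit:

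- "The SAS PROC MI procedure will be used for multiple imputations on the 6 month 6MWT distance, with 20 imputations".
- The exception is for "individuals unable to perform the 6MWT test at 6 months i.e. those who did not perform a 6MWT or died prior to 180 days", who "will have their value imputed as the worst possible 6MWT distance which is 0 meters".
- For the baseline walk, "any missing baseline 6MWT distance will be imputed as overall mean to allow full ITT population to be included in primary analyses".

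The part of section 4.4.1 on secondary endpoints deals only with the CV composite and event dates. The tipping-point analyses cover the 6-month walk (sections 5.3.1.2 and 5.3.1.8) and the top secondary outcome (section 5.3.2.2). None covers the 12-month walk.

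**The concern.** The label says all randomized participants, but the rule admits only those with both walks. People who died, could not walk or missed the 12-month visit drop out of the analysis, and so does any information from their 6-month walk.

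The primary analysis treats the same measure at 6 months differently. Living participants without a 6-month walk stay in through imputation or a 0 m score, and participants who die stay in through the death tier. If the 6-month and 12-month results differ, a reader cannot tell a change in effect from a change in who was analysed.

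Participants who are declining are plausibly more likely to miss the 12-month walk. Leaving them out would make average function look better than it is in both arms and could shift the difference between arms. Functional capacity is the trial's stated secondary objective (SAP section 1.1.2), so the reading of this endpoint matters even though it is supportive.

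**Working it through.** **1. Is the gap filled elsewhere?** No. Section 4.4.1 limits multiple imputation to the 6-month distance, section 5.5 requires both walks, and no sensitivity analysis addresses the 12-month walk.

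**2. How many would be excluded?** The only missing-walk figure is the 15% at 6 months in SAP section 1.4 (unable to perform, or lost to follow-up). It is a planning input, so there is nothing to reproduce it from, and its overlap with deaths is not defined. The other inputs, also from section 1.4, are 12-month deaths of 8% (control) and 6.8% (treatment), loss of 2.5% a year, and N = 3014 allocated 1:1. Pooled deaths are (8% + 6.8%)/2 = 7.4%; half a year gives 3.7% deaths and 1.25% loss.

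| Assumption about the 15% | Formula | Excluded share | Of 3014 |
|---|---|---|---|
| Already covers everything to month 12 | 0.15 | 15.0% | 452 |
| Covers events to month 6; add half a year of deaths | 1 − 0.85 × 0.963 | 18.1% | 547 |
| As above, plus half a year of loss | 1 − 0.85 × 0.963 × 0.9875 | 19.2% | 578 |
| Applies to 12-month survivors; add all deaths | 1 − 0.926 × 0.85 | 21.3% | 642 |
| As above, plus half a year of loss | 1 − 0.926 × 0.85 × 0.9875 | 22.3% | 671 |

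The range is about 15–22%. In the 21.3% case, 0.926 × 15% = 13.9 points are living participants without a walk and 7.4 points are deaths. The arms then differ little: 1 − 0.92 × 0.85 = 21.8% in control and 1 − 0.932 × 0.85 = 20.8% in treatment.

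**3. Power and precision.** With the planning values of 18 m and SD 90 m (set for 6 months, carried to 12 months as an assumption) and two-sided 0.05, power is 0.999 at 15% excluded and 0.998 at 22.5% excluded. At 22% excluded, n per arm is 1507 × 0.78 = 1175. The standard error is 90 × √(2/1175) = 3.7 m, against 90 × √(2/1507) = 3.3 m with everyone, a ratio of √(1507/1175) = 1.13.

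**4. Bias if missingness follows 6-month decline.** Simulation with 1507 per arm, true difference 18 m, SD 90 m and 22% missing, where the log-odds of a missing 12-month walk rise with each metre of decline at 6 months. The 6-to-12-month correlation and the dropout slope are assumptions.

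- Correlation 0.6, slope 0.01 per metre: complete-case difference 16.8 m, against 17.9 m when missing 12-month values are predicted from the 6-month walk. The complete-case control mean change is about +10 m against a true 0.
- Correlations 0.4–0.8, slopes 0.005–0.02: complete-case difference 14.9–18.2 m, imputed 17.6–18.4 m, control mean change +3 to +21 m.
- Correlations 0.3–0.8, slopes 0.005–0.01 only: the complete-case difference is 0.2–1.5 m below the full-data difference, always towards the null.

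The largest shift, 18 − 14.9 = 3.1 m, needs the steeper dropout.

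**The case against.** The strongest reply is that this is a deliberate, pre-specified rule for a supportive endpoint tested without multiplicity adjustment. In section 5.5, ITT only can be read as meaning that the analysis is not repeated in the per-protocol set, as it is for the primary and top secondary outcomes. A mean change at 12 months and a rank-based tier at 6 months are also different estimands, so they need not share missing-data rules. The inflation of within-arm change largely cancels between arms, and what is left works against FCM: up to 1.5 m is below half a standard error of 3.7 m. Section 4.1 also promises distribution curves of 6MWT change at both visits.

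Most of this stands and limits the weight of the point. It does not remove the gap: the section 2.1 definition is all randomized participants, the rule analyses a subset, and no sensitivity analysis shows what that subset does to the result.

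A caution about borrowing section 4.4.1 also stands. It defines inability to include anyone who did not perform a walk. Read literally, that covers almost every missing walk, so the definition must be settled before it is reused.

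Three stronger readings are tempting but unsupported:

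- *A fifth of participants will be dropped.* No 12-month figure is stated; 15–22% is a projection.
- *The primary keeps all these people by imputation.* It keeps deaths by ranking them on survival time, and its imputation concerns a different visit.
- *Excluding deaths hides 3–4 m of benefit*, from 0.012 × (250 to 350 m). This omits the 18 m effect lost among those who die. The net difference would be 0.932 × 18 + 0.012 × (250 to 350) = 19.8–21.0 m, a shift of 1.8–3.0 m. It rests on a baseline mean the documents do not give, and the 0 m score never decides a dead participant's rank in the primary.

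**Conclusion.** The point holds as a worthwhile, low-cost improvement. Section 5.5(1) is an observed-case analysis under an ITT label, and the SAP has no other provision for missing 12-month walks. The excluded share is projected at 15–22%. The bias figures rest on assumed correlations and on missingness driven by 6-month decline: several metres or more in within-arm change, usually about 0–1.5 m towards the null in the treatment difference, and up to about 3 m with steeper dropout.

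A reader might infer that the trial's conclusions are at risk. The documents do not support that: the endpoint is supportive, power exceeds 0.99 at the planning effect either way, and in these scenarios the complete-case result understates benefit.

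**What to change.** In section 5.5(1):

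- For participants alive at 12 months, multiply impute a missing 12-month distance from baseline distance, observed 6-month distance, treatment and region, and pool with Rubin's rules, using the PROC MI steps already in section 4.4.1.
- Say plainly that this main analysis is among participants alive at 12 months.
- Keep the both-walks regression as a sensitivity analysis, labelled observed-case.
- Add one sensitivity analysis that scores death or inability to walk as 0 m, with inability defined separately from a missed visit. This scoring is debatable for a mean difference, so it belongs only here.

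Apply the same approach to the 12-month analysis in section 5.7(11). For the 6-month analyses in 5.7(4) and (12), which carry the same both-measurements rule, reuse the existing 6-month imputation once inability is defined.

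The cost is SAP wording and modest programming, with no new data. The downside is one further assumption: that 12-month walks are missing at random given the 6-month walk and the other model terms.
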